## 2.6 Sample Size and Power

Table 3 shows power to test the non-inferiority of the seroprotective response to each of the serogroups A, C, W and Y elicited by the NmCV-5 vaccine, relative to the seroprotective response elicited by the MenACWY-TT vaccine, when administered as a single dose at either 9 months of age or 15 months of age. These calculations assume a non-inferiority margin of -10% (-0.1) for a one-sided hypothesis test, with a 2.5% Type I error rate, and using the Miettinen-Nurminen method for estimation of the 95% CI for the difference in proportions [1, 2]. The resulting power correspond to the sample size of at least 183 and 366 evaluable participants in each of the MenACWY-TT and NmCV-5 arms, respectively, where this target sample size results from the following assumptions:

- At least 600 enrolled participants will be randomly assigned to receive the study vaccine at 9 months of age and
- Among those randomized to receive the study vaccine at 15 months of age, at least 600 participants will receive it at the scheduled visit.
- For each vaccination age, participants will be randomly assigned, in a 1:2 ratio, to receive the MenACWY-TT or the NmCV-5 vaccine.
- At least 92.5% of the 600 enrolled and vaccinated participants will be followed up and contribute a sample for assessment at their Day 29 visit.

**Table 3: Power to test non-inferiority of the proportion of participant with seroprotective response at Day 29 for serogroup A, C, W and Y, for a non-inferiority margin of -10% (-0.1) and a sample size of at least 183 and 366 evaluable participants in MenACWY-TT and NmCV-5 arms, respectively.**

Serogroup	Proportion of seroprotective response in MenACWY-TT arm	Difference in proportion of seroprotective response (NmCV-5 – MenACWY-TT)		Power
		Under the Null (H0)	Under the Alternative (H1)	
A	0.95	-0.1	0	99.97%
C	0.95	-0.1	0	99.97%
W	0.90	-0.1	0	97.50%
Y	0.90	-0.1	0	97.50%

Finally, calculation of Power in Table 3 is based on assumed proportions of seroprotective response in the MenACWY-TT arms that are consistent with, if somewhat more conservative than, to those reported in the literature.

Power calculations were performed computationally, based on the exact distribution of the primary endpoint of interest under the alternative hypothesis. The probability of each combination of outcomes in the active and control arms was obtained under the assumption that they follow independent binomial distributions. The power of the test was calculated as the sum of probabilities of those scenarios where the outcomes meet the non-inferiority criterion. A simulation was also conducted to corroborate the results.

Table 4 shows power to test the non-inferiority of the seroprotective response to serogroup X. Unlike serogroups A, C, W and Y, non-inferiority of the vaccine for serogroup X will be based on the difference in the proportion of participants randomized to receive NmCV-5 with seroprotective response to serogroup X minus the proportion of participants randomized to receive MenACWY-TT with seroprotective response to the serogroup with the lowest proportion of seroprotective response. Thus, for this test, and consistent with our assumptions listed above, we assume that the lowest proportion of seroprotective response in the MenACWY-TT will be 90% or higher.

**Table 4. Power to test non-inferiority of the proportion of participant with seroprotective response at Day 29 for serogroup X, when compared to lowest seroprotective response rate among A, C, W, Y serogroups, with a non-inferiority margin of -10% (-0.1) and a sample size of at least 183 and 366 evaluable participants in MenACWY-TT and NmCV-5 arms, respectively.**

Serogroup	Lowest Proportion of seroprotective response among Serogroups A, C, W, Y in MenACWY-TT arm	Difference in seroprotective response (Serogroup X in NmCV-5 - lowest proportion among Serogroups A, C, W, Y in MenACWY-TT)		Power
		Under the Null (H0)	Under the Alternative (H1)	
X	0.90	-0.1	0	97.50%

Under the assumption that the test statistics used for the five non-inferiority tests described above are independent, the power to declare overall non-inferiority of NmCV-5 relative to MenACWY-TT at a given vaccination age is calculated to be at least 92.6%. We note, however, that this is a conservative assumption and, given the likely correlation between seroprotective response rates among all the serogroups, the overall power may be higher.

### **3 GENERAL DATA ANALYSIS CONSIDERATIONS**

#### **3.1 Timing of analyses and reporting**

The main statistical analyses of the primary and secondary immunogenicity endpoints (up to Day 29 visit) and of secondary safety endpoints (up to 6 months of follow-up) will be completed before the end of the study, as soon as the relevant data is available for each of the age groups. Results from these statistical analyses will be summarized in two reports (one per age group), which may be shared with WHO as part of the PQ process.

A first report to be submitted to WHO will include the analysis of primary and secondary endpoints for participants assigned to receive the study vaccine at 9 months of age (Group 1). This report will be produced after the relevant data from all participants in Group 1 through Visit 4 (Study Day 181) has been entered into the study database and appropriate data quality processes have been completed.

A second report to be submitted to WHO will include the analysis of primary and secondary endpoints for all participants assigned to receive the study vaccine at 15 months of age (Group 2). This report will be produced after the relevant data from all participants in Group 2 through Visit 4 (Study Day 181) has been entered into the study database and appropriate processes to ensure data quality have been completed.

The reports described above (which will be referred to as “WHO Reports”) will provide group level results without blinding or masking of the vaccine arms. The analyses will be conducted by the designated unblinded statistician, after the appropriate processes to ensure data quality are completed. The reports can be made available to a limited number of study team members for review, prior to submission to WHO. The list of study members with access to each report should be pre-approved by DMID and IDCRC representatives.

Version 1.0 of this Statistical Analysis Plan (SAP) will be finalized prior to the analyses for the WHO reports being conducted. Any changes or additions to analyses specified here will be properly documented and reported as “post-hoc” when reported.

A final study report will be completed when all primary and secondary safety, clinical, and immunological endpoint data, cumulated up to the end of the study, are available. Depending on the availability, analysis of tertiary and exploratory endpoints may be reported in the final study report, as an addendum to the final study report, in separate reports or in journal manuscript(s).

Additional reports describing immunogenicity endpoints at Day 181 (part of tertiary objectives), either for Group 1 only or for both Group 1 and Group 2, may be produced prior to the final study report, subject to approval from IDCRC and DMID.

For reporting of endpoints relevant to DSMB reviews, see Section 4.1.

## 3.2 Analysis Sets

Unless otherwise specified, each of the following definitions refers to two analysis sets: one for Group 1 (participants randomized in Step 1 to receive the study meningococcal vaccine at 9-11 months of age) and one for Group 2 (participants randomized in Step 1 to receive the study meningococcal vaccine at 15-17 months of age).

In cases where an analysis set has also been defined in Section 9 of the Protocol, the definition provided here will supersede that of the protocol.

### 3.2.1 Modified Intent-to-Treat (mITT) Analysis Sets

All participants who were randomized at Step 1 and Step 2 and who received a study meningitis vaccine (NmCV-5 or MenACWY-TT). Participants who were randomized at Step 1 and Step 2 but did not receive a study meningitis vaccine will be excluded. The analyses for this analysis set will be conducted according to the age group as assigned in Step 1 randomization (regardless of participants being vaccinated outside of the assigned age range) and according to the vaccine arm as assigned in Step 2 randomization (regardless of the actual meningitis vaccine received). Participant's observations will be included in the analysis according to the study visit in which they were collected, regardless of the visit being conducted out of the visit window.

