9.6 Analysis Plan

This section describes the statistical analyses for the primary and secondary endpoints. Analysis of tertiary and exploratory endpoints will be described in the Statistical Analysis Plan.

The main statistical analyses of the primary and secondary immunogenicity endpoints (up to Day 29 visit) and of secondary safety endpoints (up to 6 months of follow-up) will be completed before the end of the study, as soon as the relevant data is available for each of the age groups. Unblinded results (through grouped analysis) from these statistical analyses will be summarized in at least two study reports (one per age group), which will be submitted to WHO, as these data are critical for timely WHO-PQ review process.

The analyses described above may also be available for presentation and publication to inform the scientific community. Publication of manuscripts may occur at the discretion of the sponsor in accordance with DMID's Expanded Distribution of Clinical Research Endpoint Data Policy.

The Clinical Study Report (CSR) will be completed when all primary and secondary safety, clinical, and immunological endpoint data, cumulated up to the end of the study, are available.

Any available data from the exploratory endpoints may also be included. Additional exploratory endpoint data may be included in an addendum to the CSR, publication of manuscript(s), or other report.

The Safety Analysis Set will include all participants who received the NmCV-5 or MenACWY-TT vaccine at the randomly assigned vaccination age. All safety data from participants in the Safety Analysis Set will be analyzed according to the vaccine group to which the participant was randomized. In the rare instance that a participant receives the wrong intervention vaccine, the Statistical Analysis Plan (SAP) will address how to analyze the participant's safety data.

The Immunogenicity Analysis Set will include all participants who receive the expected meningococcal vaccine, within the randomly assigned age and for whom post-vaccine immunogenicity data is available at least at one timepoint post-vaccination. Analyses of primary and secondary immunogenicity endpoints will be conducted in the Immunogenicity Analysis Set.

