## 5 GENERAL ANALYSIS METHODS

The following descriptive statistics will be used to summarize continuous outcomes: number of non-missing values, mean and standard deviation, median, interquartile range, and range (minimum and maximum). Descriptive statistics for categorical endpoints may include number of non-missing values, frequencies, relative frequencies, and percentages.

Additionally, descriptive summaries of immunogenicity data may include Geometric Means (GM), proportion of participants showing levels above a certain pre-defined cutoff or proportion of participants achieving a pre-specified increase from baseline.

For selected binary endpoints, 95% exact binomial Confidence Intervals (CI), calculated using the Clopper-Pearson method, may be presented. For GM, the corresponding 95% CIs will be based on the log-transformed endpoint and calculated based on a t-distribution with degrees of freedom equal to n-1 (where n denotes the number of observations).

To identify the different randomization arms/groups, the following naming conventions will be used in this SAP and for reporting and displaying of the data analyses.

- “Participants assigned to receive vaccine at 9 months of age” or “Group 1” will be used to describe those screened and enrolled participants who at Step 1 randomization are assigned to receive their meningitis vaccine immediately, noting that the eligibility age range is 9 to 11 months of age.
- “Participants assigned to receive vaccine at 15 months of age” or “Group 2” will be used to describe those screened and enrolled participants who at Step 1 randomization are assigned to receive their meningitis vaccine about 6 months after Step 1 randomization, noting that the eligibility age range is 15 to 17 months of age.
- Within the two groups described above, the term “by vaccination arm” or simply “by arm” will refer to the groups resulting from random vaccine assignment performed at Step 2 randomization (NmCV-5 vs MenACWY-TT).

All summaries and statistical analyses will be produced using SAS statistical software, Version 9.4 of the SAS System for Linux, Copyright © 2013 SAS Institute Inc [3] (SAS and all other SAS Institute Inc., product or service names are registered trademarks or trademarks of SAS Institute Inc., Cary, NC, USA). The R statistical software [4] can also be used to produce (or replicate) selected figures.

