### **9.3 Serious Adverse Events**

Secondary Endpoint: All Serious Adverse Events (SAE), reported during the first 6-months of follow-up period after meningococcal vaccination.

Tertiary Endpoint: All SAEs, reported through 2 years of follow-up or during the entire study period, after meningococcal vaccination.

Unsolicited Adverse events that are reported as Serious Adverse Events (SAEs) according to ICH/GCP or Protocol will be collected from the time of Step 2 randomization and vaccination to through study termination, up to 2 years after meningococcal vaccination. For participants randomized to receive their meningococcal vaccine at 15-17 months, SAEs occurring after Step 1 randomization visit but prior to Step 2 randomization visit may be collected but will not be included in the evaluation of vaccine safety endpoints. Their reporting is described in section 9.4.1.

The secondary endpoint includes all SAEs reported in scheduled or interim (unscheduled) visits after receipt of study meningitis vaccine and with date of onset up to and including Study Day 181.

The tertiary endpoint (to be reported only at the end of the study) includes all SAEs collected in scheduled or interim (unscheduled) visits after receipt of study meningitis vaccine and up to and including the last scheduled Study Visit (Visit 5, scheduled for Study Day 730 ± 45 days).

Analysis Set: mITT Analysis Set

Approach: Serious Adverse Events (SAE), as collected in the Adverse Event eCRF, will be reported in listings, by age and meningococcal vaccination arm. The listing will include Subject ID, MedDRA Preferred Term, AE description verbatim, Severity, Relationship to Study Product, Study Visit where the SAE was reported, Onset Date, time to Onset Date (in days) from study meningitis vaccination, Outcome Date, Duration Days, Action Taken with Study Product, Other Actions, Status/Outcome, Criteria that makes the AE and SAE, if the AE meet criteria for Suspected Unexpected Serious Adverse reaction (SUSAR), if the event was evaluated for halting criteria and if the AE is a worsening of a baseline medical condition.

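### Safety results stay under the assigned vaccine even when an infant got the other one, and the listings do not show which vaccine was given

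*SAP*

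**What the plan says.** Protocol 9.6 states the default: "All safety data from participants in the Safety Analysis Set will be analyzed according to the vaccine group to which the participant was randomized". The next sentence sets one case aside: "In the rare instance that a participant receives the wrong intervention vaccine, the Statistical Analysis Plan (SAP) will address how to analyze" that participant's safety data.

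The SAP has no separate safety set. SAP 3.2 says that its set definitions replace those in section 9 of the protocol. SAP 3.2.1 defines the mITT set as "All participants who were randomized at Step 1 and Step 2 and who received a study meningitis vaccine (NmCV-5 or MenACWY-TT"), and analyses it "according to the vaccine arm as assigned in Step 2 randomization (regardless of the actual meningitis vaccine received"). SAP 9.1 (solicited events), 9.2 (unsolicited events) and 9.3 (SAEs to Day 181 and to two years) each name this set and no other; in 9.3 the entry reads "Analysis Set: mITT Analysis Set".

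SAP 5 says that the phrase by arm "will refer to the groups resulting from random vaccine assignment performed at Step 2 randomization (NmCV-5 vs MenACWY-TT"). Under SAP 9.3, SAEs "will be reported in listings, by age and meningococcal vaccination arm". The fields specified for the listings in 9.2 and 9.3 cover severity, relatedness, dates, actions, outcome, SUSAR status and halting evaluation, but not the vaccine the infant received.

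**The concern.** The secondary safety objective asks about the safety and tolerability of a dose of each product, which is a question about exposure. Under the plan, an infant assigned to MenACWY-TT who was given NmCV-5 has every reaction counted in the MenACWY-TT column, and the reverse holds for the opposite error.

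The problem is sharpest for related events. The main unsolicited-event table in SAP 9.2 counts events judged related to study product. For a misdosed infant, that judgement concerns the vaccine injected while the column heading names the other one. A reader of the SAE listing could not see the mismatch from the fields specified. The unblinded group-level results are intended for WHO as part of the pre-qualification review (SAP 3.1).

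**Working it through.** The plan gives no figure on this point, so there is none to reproduce. The check has two parts.

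**1. Tracing the rule**

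- Who is in the set: anyone randomized at both steps and given either study vaccine (SAP 3.2.1). Misdosed infants are therefore included.
- Which column they fall in: the assigned one (SAP 3.2.1 and SAP 5).
- Which safety endpoints use the set: all of them (SAP 9.1, 9.2, 9.3).
- Whether anything offsets the rule: neither document has an as-treated safety analysis or a sensitivity analysis by vaccine received. The per-protocol set requires receipt of the assigned vaccine (SAP 3.2.2), but no safety endpoint uses it.
- Whether the vaccine received is known: the per-protocol criterion can be applied only if it is.

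**2. Size**

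Inputs: 400 NmCV-5 and 200 MenACWY-TT infants per age group (SAP Table 1). The number misdosed is not given, so the values of m below are assumptions.

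*One affected infant with an event.* The shift is 1/200 = 0.5 percentage points in the control arm and 1/400 = 0.25 points in the NmCV-5 arm.

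*A single rare event after NmCV-5 in an infant assigned to MenACWY-TT.*
- As planned: 1/200 (0.5%) under MenACWY-TT and 0/400 under NmCV-5.
- By vaccine received, if this is the only error: 0/199 under MenACWY-TT and 1/401 (0.25%) under NmCV-5.

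*Effect on the difference between arms.* Suppose m infants in each arm receive the other vaccine, and the true rates are rA (NmCV-5) and rB (MenACWY-TT). The as-assigned rates are

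- NmCV-5: [(400 − m)·rA + m·rB] / 400
- MenACWY-TT: [(200 − m)·rB + m·rA] / 200

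Subtracting gives (rA − rB) × (1 − m/400 − m/200).

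| m per arm (assumed) | Share of true difference kept |
|---|---|
| 1 | 1 − 0.0025 − 0.005 = 99.25% |
| 2 | 1 − 0.005 − 0.01 = 98.5% |
| 5 | 1 − 0.0125 − 0.025 = 96.25% |
| 10 | 1 − 0.025 − 0.05 = 92.5% |

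Example with assumed true rates of 10% and 5% and m = 5:
- NmCV-5: (395 × 0.10 + 5 × 0.05)/400 = 39.75/400 = 9.94%.
- MenACWY-TT: (195 × 0.05 + 5 × 0.10)/200 = 10.25/200 = 5.13%.
- Difference: 4.81 points instead of 5.

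Rates of common events therefore hardly move. A single rare event, by contrast, changes column completely.

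**The case against.** The strongest reply is that the plan is deliberate and complete. As-randomized analysis is the protocol's own default for safety data. The protocol asked the SAP to settle wrong-vaccine cases, and SAP 3.2.1 does so in advance and without ambiguity. This stands: there is no contradiction between the documents and no gap in the set definition. A reader might infer that the SAP overrode the protocol, or that it carried an immunogenicity convention over to safety. Neither is supported. The primary immunogenicity analyses use the per-protocol set, which excludes misdosed infants, and mITT is secondary there (SAP 8.2.1, 8.2.2).

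The second reply is that safeguards exist. SAEs are listed one by one. Any related SAE halts enrolment and vaccination for DSMB review (Protocol 7.6.1). Unblinding information is supplied for an SAE that must go to regulators (Protocol 9.4.2). All recorded deviations are listed with a description (SAP 6.6). These make it likely that a wrong-vaccine SAE would be noticed. They do not move the event to the right column, and they give much less cover to solicited reactions and non-serious events.

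The third reply is rarity. It limits the importance of the point, but it is no reason to prefer the as-assigned rule for safety, since the alternative changes nothing when no error occurs.

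**Conclusion.** The point holds as an inexpensive improvement to a clear and pre-specified rule. If an infant receives the other study vaccine, all of that infant's safety data are shown under a product the infant did not get, and the listing fields would not reveal it. The size depends on how many such errors occur, which the documents do not say beyond calling them rare. At 0.5 or 0.25 points per affected infant with an event, the effect on common event rates is negligible. What remains is the attribution of a single related or serious event, partly covered by the individual SAE listings, DSMB review and the deviation listing.

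A reader might go further and infer that one misattributed SAE would change the trial's safety conclusion. The documents do not support that: the safety analysis is descriptive with no hypothesis test (Protocol 9.2), so no decision rule could flip, and a related SAE would be examined individually.

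**What to change.** In SAP 3.2, define a Safety Analysis Set with the same infants as the mITT set (randomized at both steps and given a study meningococcal vaccine), analysed by vaccine actually received. Keeping the two-step condition leaves out the Group 2 infants who are given open-label MenACWY-TT and not followed. State openly that this departs from the as-randomized default in Protocol 9.6. Name the new set in SAP 9.1 to 9.3. Add the vaccine received and a misallocation flag to the adverse event and SAE listings. Leave mITT as assigned for the secondary immunogenicity analyses.

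The cost is SAP wording and one extra variable in the listings, with no new data collection. Under SAP 3.1, changes to the specified analyses must be documented and reported as post hoc, so the amendment is best made before the safety results are unblinded. If no infant was misdosed, every table is the same under either rule.

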### 3.2.2 Per Protocol (PP) Analysis Sets

These sets will include participants who:

- Are not later found to have been ineligible at the time of enrollment.
- Completed Step 1 and Step 2 randomizations.
- Received the study meningitis vaccine at the appropriate age range, as assigned in Step 1 randomization:
  - At least 9 months and no older than 12 months ( $9.0 \leq \text{age} < 12.0$ ) for participants randomized to Group 1.
  - At least 15 months and no older than 18 months ( $15.0 \leq \text{age} < 18.0$ ) for participants randomized to Group 2.

Inclusion of participants vaccinated outside the assigned age range may occur only if approved by a protocol deviation review committee.

- Received the study meningitis vaccine that was assigned at Step 2 randomization.
- Received the scheduled EPI concomitant vaccines. For participants in Group 1, this means receiving the Measles-Rubella (MR) and Yellow Fever (YF) vaccine concurrently with the study meningitis vaccine when at least 9 months and no older than 12 months. For participants in Group 2, this means having received a first MR vaccine as scheduled at about 9 months of age (at the time of enrolment and Step 1 randomization) and a second MR vaccine concurrently with the study meningitis vaccine when at least 15 months and no older than 18 months of age.
- Had a blood specimen collected at Visit 3, with the collection date (as reported in the "Specimen Collection – Blood" eCRF) between Study Day 29 and Study Day 43 (29+14). This is a wider window than the one specified in the protocol for Visit 3 (Day 29 + 7 days). The decision to extend this window was to avoid over-exclusion of participants considering that rSBA titers to meningitis serogroups are expected to reach peak levels before Day 29 and to remain relatively stable (or at least not to decrease significantly) for several weeks. Inclusion of participants with specimen collection outside the above specified window may occur only if approved by a protocol deviation review committee.
- Had a successful/valid rSBA value determined (and provided) by the corresponding Laboratory for at least one of the meningitis serogroups tested (A, C, W, Y or X).
- Did not have a reported protocol deviation (in addition to those listed above) that could impact the meningitis immunogenicity endpoints, as determined by a protocol deviation review committee.

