A secondary immunogenicity objective is to demonstrate the superiority of the NmCV-5 vaccine to elicit seroprotective response to the meningococcal serogroup X. To achieve this objective, the study will test a null hypothesis of the difference in the proportion of participants with vaccine seroprotective response to serogroup X equal or less than 30% (0.3) versus an alternative hypothesis of the difference in proportions of 30% or greater. Vaccine seroprotective response to serogroup X has been defined above, with non-inferiority declared if the lower bound of the two-sided 95% confidence interval for the difference in proportion of participants with seroprotective response is at or above 10%.

The secondary objective related to the immunogenicity of EPI vaccines is to demonstrate that seroprotective response elicited by EPI vaccines when co-administered with NmCV-5 is non-inferior to the seroprotective response elicited by these same vaccines when co-administered with MenACWY-TT. The study will test the null hypothesis that, for each EPI vaccine, the difference in the proportion of participants showing seroprotective response (in the NmCV-5 arm relative to the MenACWY-TT arm) is equal or less than 10% (-0.1) in favor of the alternative hypothesis that the difference is greater than -10% (0.1). The seroprotective response to measles vaccination is defined as anti-measles IgG concentration > 90 mIU/mL, the seroprotective response to yellow fever vaccine is defined as neutralizing antibody titers \geq 1:8, and the seroprotective response to rubella vaccine is to be according to the manufacturer's specified cutoff, for a commercially-available and validated rubella IgG assay, all from samples collected at Day 29 visit. For each EPI vaccine, non-inferiority will be declared if the lower bound of a two-sided 95% confidence interval of the difference in proportion of participants with seroprotective response is above -10% (-0.1).

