### **3.3.2 Non-inferiority hypothesis tests**

Endpoint specific one-sided non-inferiority hypothesis tests will be conducted under a 2.5% significance level. Each non-inferiority test will be evaluated by calculating a two-sided 95% confidence interval for the difference in proportions of participants with the specific response and comparing the lower bound of the

CI to a non-inferiority margin (otherwise noted, the margin is -0.1 and will be expressed as -10%). No p-values will be reported.

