### 8.3.4 Non inferiority of the seroprotective response to yellow fever vaccine

Hypothesis: Null hypothesis: The immune response to yellow fever at Day 29 elicited by the yellow fever vaccine when co-administered with one dose of NmCV-5 is inferior to the immune response elicited by the yellow fever vaccine when co-administered with one dose of MenACWY-TT.

Alternative hypothesis: The immune response to yellow fever at Day 29 elicited by the yellow fever vaccine when co-administered with one dose of NmCV-5 is non inferior, by a pre-specified margin, to the immune response elicited by the yellow fever vaccine when co-administered with one dose of MenACWY-TT.

Endpoints: Seroprotective response to yellow fever vaccine at Day 29 post vaccination, defined as yellow fever neutralizing antibody titers  $\geq 10$ .

Strata: Not applicable for this endpoint.

Analysis Set(s): Per Protocol (PP) Analysis Set (defined in Group 1 only).

Approach: The proportion of infants with a seroprotective response to yellow fever vaccine at Day 29 will be calculated as:

$$p_V^{YF} = \frac{\sum_{i=1}^{N_V} I(F_i^V \geq 10)}{N_V} = \frac{n_V^{YF}}{N_V},$$

where V indicates arm (NmCV-5 vs. MenACWY-TT),  $N_V$  is the number of infants in the analysis set randomized to arm V and  $F_i^V$  is the yellow fever neutralizing antibody titers at Day 29 for  $i^{\text{th}}$  infant in arm V.

The NmCV-5 co-administered YF vaccine will be deemed non-inferior to the MenACWY-TT co-administered YF vaccine in eliciting seroprotective response to

yellow fever if the lower limit of the 95% confidence interval for  $p_{NmCV-5}^{YF} - p_{MenACWY-TT}^{YF}$  excludes -0.10.

Confidence Intervals will be calculated using the Miettinen-Nurminen method [1, 2].

Reporting:	The number ( $n_V^{YF}$ ) and proportion ( $p_V$ ) of participants with seroprotective response will be provided (by arm), along with point and 95% CI estimates of the difference in proportions ( $p_{NmCV-5}^{YF} - p_{MenACWY-TT}^{YF}$ ).
Graphical display:	Point estimates and 95% CIs for $p_{NmCV-5}^{YF} - p_{MenACWY-TT}^{YF}$ will be displayed graphically in a forest plot, with the non-inferiority margin (expressed as -10%) included as reference.

### 8.3.5 Level of rSBA titers and seroresponse at Day 29

A descriptive analysis of the distribution of rSBA titers at Day 29 will be conducted, as follows:

Endpoint:	rSBA titers against meningococcal serogroups A, C, W, X and Y, from samples collected at Visit 3 (Study Day 29).

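### The measles, rubella and yellow fever tests run only on a per-protocol set whose deviation screen and assay rule look at meningitis endpoints alone, with no mITT check

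*SAP*

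**What the plan says.** SAP 8.3.2 (measles) and 8.3.3 (rubella) name the per-protocol (PP) set and no other. SAP 8.3.4 (yellow fever) names the "Per Protocol (PP) Analysis Set (defined in Group 1 only", again with nothing beside it. By contrast, the primary rSBA tests (SAP 8.2.1, 8.2.2) and the secondary serogroup X superiority test (SAP 8.3.1) each have a second analysis on the mITT set.

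The PP set is defined once, in SAP 3.2.2. Three of its rules are written around meningitis:

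- Assay rule: "Had a successful/valid rSBA value determined (and provided) by the corresponding Laboratory for at least one of the meningitis serogroups tested". There is no matching rule for the measles, rubella or yellow fever assays.
- Residual deviation screen: an infant is removed for a further deviation only if it is one "that could impact the meningitis immunogenicity endpoints, as determined by a protocol deviation review committee".
- Sampling window: Day 29 to 43, wider than the protocol's Day 29 + 7, and justified only by how rSBA titres behave over time.

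Two other rules do protect the EPI tests. MR (and YF in Group 1) must be given together with the study vaccine and in the age range, and Group 2 must also have had the first MR dose. Infants later found to have been ineligible at enrolment are removed, and earlier measles vaccination is an exclusion criterion (Protocol 4.1.2).

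**The concern.** Non-interference with routine vaccines is in the trial's title and is one of its stated purposes for WHO pre-qualification. A per-protocol set is meant to keep out departures that could blur a real difference between arms. Here that screening is only partly done for the EPI endpoints: receipt and timing of MR and YF are checked, but other departures are judged by their effect on a different endpoint. If deviations that make the EPI response independent of the meningococcal arm stay in, they pull the arms together, which helps a non-inferiority claim. In the other direction, infants with usable EPI data can be lost for reasons unrelated to those data. With only one analysis set planned, the results would show neither effect.

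**Working it through.** **1. Which infants does the text keep or drop?** Applying SAP 3.2.2 literally to the EPI tests:

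| Case | Outcome under SAP 3.2.2 |
|---|---|
| MR or YF missed, not concurrent, or out of age range | Dropped (EPI receipt rule) |
| Measles vaccine before enrolment, discovered later | Dropped (ineligible at enrolment) |
| MR or YF given on time after a storage or handling breach (limits in Protocol 3.1.2 and 3.3) | Kept, unless judged to affect meningitis endpoints |
| Extra measles dose outside the study after enrolment | Kept, on the same condition |
| Valid EPI result, all five rSBA results invalid | Dropped |
| Group 1 infant who missed only YF | Dropped from the measles and rubella tests too |

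The extra-dose case is not fanciful. Protocol 1.1.2 (note to Table 3) says a second measles dose is being introduced in certain locations in Mali, and Group 2 waits about six months between enrolment and study vaccination.

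**2. Denominator.** SAP 8.3.2 to 8.3.4 divide by N_V, the number of infants in the analysis set in that arm. PP entry needs no EPI result, so N_V can include infants without one, and read literally they count as non-responders. SAP 8.1 treats invalid assay results as missing, but the complete-case rule in SAP 3.3.4 covers only the primary endpoints on mITT. The EPI denominator is therefore unsettled.

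**3. Inputs for the size.** SAP 3.3.2: "Endpoint specific one-sided non-inferiority hypothesis tests will be conducted under a 2.5% significance level". Protocol 9.2: "For each EPI vaccine, non-inferiority will be declared if the lower bound of a two-sided 95% confidence interval" for the difference lies above −10 points. SAP 2.6: "at least 183 and 366 evaluable participants in each of the MenACWY-TT and NmCV-5 arms", and "participants will be randomly assigned, in a 1:2 ratio, to receive the MenACWY-TT or the NmCV-5 vaccine". Neither document gives EPI response rates or deviation counts, so those below are assumptions.

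**4. Reproducing the plan's own figures.** Exact enumeration of two independent binomials (366 and 183), with success when the Miettinen-Nurminen score statistic at −0.10 exceeds 1.96, gives 99.97% at a common rate of 0.95 and 97.50% at 0.90. The five-test product is 0.9997² × 0.975³ = 0.926. All three match SAP 2.6, so the same calculation can be used for the EPI tests.

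**5. Effect of retained deviations.** Take true rates of 0.80 (NmCV-5) and 0.90 (MenACWY-TT), exactly at the margin. Let a fraction f of both arms respond at a common rate r whatever the arm:

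- NmCV-5: (1 − f) × 0.80 + f × r
- MenACWY-TT: (1 − f) × 0.90 + f × r
- Difference: −0.10 × (1 − f)

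| f in both arms (assumed) | Difference, points | False-claim rate per test (r from 0.5 to 0.95) |
|---|---|---|
| 0 | −10.0 | 2.7% |
| 2% | −9.8 | 3.1% |
| 5% | −9.5 | 3.8–3.9% |
| 10% | −9.0 | 5.1–5.6% |

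**6. Effect of dropping usable infants.** Power per EPI test with equal true rates:

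| Common rate (assumed) | 183/366 | 5% fewer | 10% fewer |
|---|---|---|---|
| 0.90 | 97.5% | 96.9% | 96.0% |
| 0.85 | 90.3% | 88.8% | 87.3% |

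Random loss therefore costs little.

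**The case against.** The strongest reply is that the PP set already handles the EPI failures most likely to matter: missed doses, doses not given concurrently, doses out of age range, and ineligible infants. The committee could also read its remit broadly. EPI administration is tabulated by arm (SAP 6.2.2) and every deviation is listed (SAP 6.6). These are secondary endpoints, and the effect is small unless deviations are common. Most of this stands. It does not supply a rule: the wording directs the committee to meningitis endpoints, and a listing does not re-run the test.

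Four stronger readings are tempting and are not supported.

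- A reader might infer that the set rests on meningitis criteria alone. The EPI receipt rule and the eligibility rule contradict that.
- A reader might infer that the protocol's plan was safer because it was broader: "Analyses of primary and secondary immunogenicity endpoints will be conducted in the Immunogenicity Analysis Set". That set does not require EPI receipt, and mITT (SAP 3.2.1) requires neither EPI receipt nor a visit window. Both would keep more diluting infants than PP does.
- A reader might infer that each 1% of infants wrongly kept moves the result by 1 point. That is a one-arm worst case. With 1% of both arms affected, a 10-point difference becomes 10 × 0.99 = 9.9, a shift of 0.1 point.
- A reader might infer that the Day 43 limit biases the EPI tests. It applies to both arms, and nothing in the documents shows that EPI antibody changes between Day 36 and Day 43.

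The rSBA drop-out route is also narrow, since all five results must be invalid.

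**Conclusion.** The point holds as a gap in the definition of the EPI analysis set, not as evidence of a biased result. Followed exactly, the SAP keeps infants whose only deviation concerns MR or YF, can drop infants with valid EPI results for unrelated reasons, leaves the EPI denominator open, and plans no second analysis set. The inflation figures assume true rates of 0.80 and 0.90, deviations equally common in both arms, and responses in affected infants that do not depend on arm. On those assumptions, one-sided error stays near 3% at 2% affected and roughly doubles at 10%. Which of these is closer to the truth cannot be told from the documents. The primary rSBA comparison is not affected.

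**What to change.** In SAP 3.2.2, or in each of 8.3.2 to 8.3.4, define the PP set for each EPI endpoint as follows:

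- Keep the existing eligibility, randomisation and study-vaccination rules.
- Require receipt of the EPI vaccine being analysed, on the existing timing rules, so that missing only YF does not remove an infant from the measles and rubella tests.
- Replace the rSBA rule with a valid Day 29 result for that EPI assay. This also settles N_V.
- Exclude deviations that could affect that EPI endpoint, as judged by the same committee.

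Add a secondary mITT analysis for each EPI test, as is done for rSBA. Its purpose is to check the PP exclusions; it does not cure dilution. A further check limited to Day 29 + 7 is optional.

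The cost is a short extra deviation review and some programming on existing data, with no new visits or blood draws. This assumes that the EPI assays are run on all available Day 29 sera. Changes made after SAP version 1.0 are to be reported as post hoc (SAP 3.1), so the change is best made before the EPI results are analysed.
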